4.2 Accountability of Study Supplies

Please refer to the pharmacy manual for information on accountability of study supplies.

4.3 Disposition of Used/Unused Product

Please refer to the pharmacy manual for information on the disposition of used/unused product.

5. Methods of Assigning Subjects to Treatment Groups

Please refer to the pharmacy manual for information on the methods of assigning subjects to treatment groups (i.e. randomization, and blinking/masking).

6. Analytic Plan, Power Analysis and Approach to Potential Challenges

Initial data analyses will inspect socio-demographic and clinical group differences as well as correlations between clinical and biological variables and specified behavioral measures. Clinical or demographic variables demonstrating a correlation with both biological and behavioral measures, will be assessed as potential confounders⁸². The EEfRT behavioral data will be analyzed using generalized estimating equation (GEE) models, according to previous studies^{30,33}. For the assessment of associations between the remaining behavioral measurements and biometric data, we will use generalized linear models, due to its greater flexibility and ability to analyze data with non-normal distributions. Group (mood disorders vs. non-psychiatric) effects will be analyzed, with age, gender, and other relevant covariates included in the models. Special considerations will be given to smoking and use psychotropic medications, given its potential effects of both reward processes and insulin signaling.

Mediation and moderation models will be assessed using regression-based, bias-corrected bootstrap tests⁸³. The main objective is to test whether there is a mediated effect of X (i.e. mood disorders) on the outcome Y (i.e. anhedonia and reward behavior) through M (i.e. insulin signaling and dopamine metabolism). If appropriate, moderated mediation models (conditional process analysis) will be used to test whether the mediation effect was contingent on a moderating variable W (e.g. obesity, medications). This method uses bootstrapping to determine bias-corrected (asymmetric) 95% confidence intervals for the indirect effects⁸⁴. Bootstrapping methods have been recently advocated, as they are based on random sampling of the data and do not make assumptions about the shape of the sampling distribution; they are also more powerful and allow for the construction of more accurate confidence intervals, relative to normal theory methods⁸³.

For the imaging analysis, statistical parametric mapping (SPM8, Wellcome Department of Cognitive Neurology, London, U.K., www.fil.ion.ucl.ac.uk/spm) will be used to preprocess the raw fMRI data. A hypothesis-driven region of interest approach will be used to investigate initially the striatum and mPFC. For the resting-state data, BOLD signal in these regions will be compared between conditions (i.e. insulin and placebo) for each subject using GEE. For the task-based data, mean percent BOLD signal change in these regions under varying reward and probability conditions will be extracted, and we will compute a set of contrasts testing the main effects of reward magnitude, reward probability, and the interaction for each subject⁷³. These first-level individual contrast maps will be fed into a second-level group (i.e. mood disorders vs. controls) and condition analysis, which will also use GEE. Association between behavioral measurements, biometric data and neuroimaging measurements will be assessed with generalized linear models. The false discovery rate (FDR) method will be used to correct for multiple comparisons and significance will be taken at a FDR-corrected threshold of p < 0.05^{86} .

Power Analysis: The primary hypothesis of this study is that anhedonic symptoms in individuals with mood disorders will be mediated by abnormalities in insulin signaling; therefore, the power analysis is based on a bias-corrected bootstrap test of mediation. Results from our preliminary data indicated that the path coefficients were mostly of medium effect sizes (e.g. $\beta \approx 0.25$ -0.35); empirical analysis indicated that in this condition a sample sizes of 116 is necessary to achieve 80% power85. To account for the possibility of subject attrition and/or inadequate measurements, we will set an initial enrollment goal of 150 subjects.

Potential Challenges and Ways to Overcome Them: The primary challenge in this study is that of recruiting and retaining 150 participants over a 3-year period. Given the experience and volume of the mood disorders clinics involved in this study, we believe that this goal is attainable. There are two potential limitations in our sample composition proposal. First, it is expected that the majority of participants recruited in tertiary mood disorders clinics will report clinically significant anhedonic symptoms. Nonetheless, it is possible that some of the subconstructs analyzed will not display satisfactory psychometric properties for contrast/comparisons. Second, we propose to pre-stratify our sample based on overweight/obesity. There is a well-documented association between adiposity and insulin sensitivity; though these are not perfectly collinear constructs. There are no, however, validated, publicly available, normative data of anhedonic symptoms, whereas gold-standard evaluations of insulin sensitivity are invasive and costly (e.g. hyperinsulinemic euglycemic clamp); therefore approximations are initially necessary. We propose to conduct a preliminary analyses after one third of the sample (n=50) is recruited and reevaluate the sample selection procedures.

A key challenge for the interpretation of results will be how to account for the role of potential confounding factors. These factors include, but are not limited to, psychotropic medications, smoking, socio-demographic characteristics, dietary and lifestyle factors. We opted for a "real-life" naturalistic treatment-seeking sample, as we seek to recruit a sample that is representative of other clinical samples. Moreover, ethical considerations preclude us from withdrawing or deferring initiation of medications. Therefore, we propose to systematically measure these confounding factors and use it as control and/or sub-stratification variables, as appropriate.

ADVERSE EVENTS

Definitions

Adverse event

An adverse event is the development of an undesirable medical condition or the deterioration of a pre-existing medical condition following or during exposure to a pharmaceutical product, whether or not considered causally related to the product. An undesirable medical condition can be symptoms (e.g., nausea, chest pain), signs (e.g., tachycardia, enlarged liver) or the abnormal results of an investigation (e.g., laboratory findings, electrocardiogram). In clinical studies, an AE can include an undesirable medical condition occurring at any time, including run-in or washout periods, even if no study treatment has been administered.

Serious adverse event

A serious adverse event is an AE occurring during any study phase (i.e., run-in, treatment, washout, follow-up), and at any dose of the investigational product, comparator or placebo, that fulfils one or more of the following criteria:

- results in death
- is immediately life-threatening
- requires in-patient hospitalization or prolongation of existing hospitalization
- results in persistent or significant disability or incapacity
- is a congenital abnormality or birth defect
- is an important medical event that may jeopardize the patient or may require medical intervention to prevent one of the outcomes listed above.

The causality of SAEs (i.e., their relationship to study treatment) will be assessed by the investigator(s). Note that SAEs that could be associated with any study procedure should also be reported. For such events the casual relationship is implied as "yes".

Recording of adverse events

AEs will be collected during each visit. At each visit, subjects will be asked if they have had any health problems since the previous visit. All AEs will be recorded appropriately, whether or not considered related to the investigational product. This will include AEs spontaneously reported by the patient and/or observed by the staff as well as AEs reported in response to a direct question e.g. "Have you had any health problems since your last visit?"

For each AE, the following parameters be described:

- start and stop date
- action taken with regards to investigational product
- outcome
- if the AE caused the patient to discontinue
- a statement if the AE fulfils the criteria for a SAE or not
- the investigator's assessment of the causal relationship between the event and the investigational product
 - intensity of the AE
 - o mild (awareness of sign or symptom, but easily tolerated)
 - o moderate (discomfort sufficient to cause interference with normal activities)
 - o severe (incapacitating, with inability to perform normal activities)

It is important to distinguish between serious and severe AEs. Severity is a measure of intensity whereas seriousness is defined by the criteria in Section. An AE of severe intensity need not necessarily be considered serious. For example, nausea that persists for several hours may be considered severe nausea, but not an SAE. On the other hand, a stroke that results in only a limited degree of disability may be considered a mild stroke but would be an SAE.

Symptoms associated with overdose should be reported as AEs. For further information regarding overdose, see section.

Pregnancy in itself is not regarded as an AE unless there is a suspicion that an investigational product may have interfered with the effectiveness of a contraceptive medication.

Follow-up of adverse events should be based upon the clinical judgement of the investigator.

Reporting of serious adverse events

Reporting of SAEs to regulatory authorities will be done by the investigator in accordance with local regulations. A copy of the report will also be sent to the manufacturer of the investigational product.

7. Anticipated Timeline

Study start-up is planned immediately after REB approval. The last six months will focus on data management, image processing and analyses. This will allow 27 months of subject recruitment and study execution, with a target of an average of 2-3 participants per site per month.

8. Personnel and Facilities

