1. Hypothesis and Specific Aims

Overarching Hypothesis: Insulin signaling is a critical neurobiological substrate of anhedonia in mood disorders

Specific Hypotheses: In individuals with mood disorders, objective and self-reported measures of anhedonia and reward behaviors are associated with alterations in insulin signaling-related molecular, cellular and neural substrates. Considering the role of insulin in the regulation of energy expenditure, we primarily hypothesize that individuals with mood disorders will display decreased willingness to make effort for rewards, relative to healthy controls; and that this abnormality will be associated with:

- a) Molecular: Differential gene and protein expression of the metabolic (i.e. PI3K/Akt) and mitogenic (i.e. Ras/MAP kinase) components of the insulin signaling pathway, as well as with components of reward-related processes (i.e. dopamine receptors and transporter)
- b) Physiology: Reduced peripheral sensitivity to insulin and corresponding metabolic correlates, including increased body mass index and dyslipidemia (i.e. peripheral insulin resistance)
- c) Neural Circuits: Diminished response to insulin in cortico-striatal networks (i.e. brain insulin resistance)

Overarching Aim: To determine the role of insulin signaling on the neurobiological substrates subserving anhedonia within individuals with mood disorders.

Specific Aims:

- a) Molecular: Assessment of components of the insulin cascade, as well as of anhedonia and reward-related processes, using a proteomics and gene expression approach;
- b) Physiology: Measurement of peripheral sensitivity to insulin and metabolic correlates, including body mass index and dyslipidemia;
- c) Neural Circuits: Evaluation of the insulin sensitivity of prefrontal (e.g. prefrontal cortex) and striatal (e.g. nucleus accumbens, ventral tegmental area) networks in the resting-state and during an effort-based decision making test, using acutely administered intranasal insulin and functional magnetic resonance imaging (fMRI);
- d) Behavioral: Measurement of willingness to make effort for rewards, as well as of other components of reward response and anhedonia, using validated behavioral tasks and clinical scales (e.g. Snaith-Hamilton Pleasure Scale SHPS).

2. Background and Rationale

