T2DM in individuals with mood disorders is between 8 and 10%, whereas the prevalence of metabolic syndrome is approximately 30%⁷. Convergent lines of inquiry indicate that mood and metabolic disorders have a bidirectional association⁸⁻¹⁰. For example, it is reported that individuals with T2DM have an approximate 2-3 fold greater risk for subsequently declaring MDD or BD¹¹. Nonetheless, the association between metabolic and mood disorders is still poorly understood. Overlapping risk factors (e.g. diet, physical activity, psychotropic medications, sleep, childhood trauma) have an important role⁶; however there is insufficient data on the extent to which these environmental factors are responsible for the mood-metabolic disorders comorbidity. Mechanistic studies have documented a role for the biological substrates of metabolic and mental disorders, such as neurostructural alterations ^{12,13}, and differences in peripheral biomarkers¹⁴. A recent genetic study identified multiple genes that are likely shared between mood and metabolic disorders; pathway analysis revealed an over-representation of genes that encode for molecules involved in dopamine signaling¹⁵. There is considerable evidence that dopamine has a core role in anhedonia and reward-related behaviors, indicating that this is a particularly promising area for further advancing the knowledge on the association of mood and metabolic disorders.

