1.4. Insulin Signaling, Anhedonia and Major Depressive Disorder

The epidemiological, phenomenological and biological associations between mood disorders and metabolic disturbances have been amply documented. The foregoing observations provide the rationale for hypothesizing that there is a neurobiological association between metabolic disorders (e.g. diabetes) and mood disorders. The devastating impact of mood and metabolic disorders on affected individuals underscores the importance of urgently understanding better the basis of this association. Anhedonia is a well-described symptom that similarly occurs in both disorders. The extant evidence of the association between insulin and dopamine signaling and the potential repercussions of disturbances in this system indicates that this is a promising target for clinical and neurobiological investigations. The interface between anhedonia and insulin represents a unique opportunity to integrate innovative and transdisciplinary lines of research in an investigative platform aiming at providing a more accurate and refined assessment of relevant mechanisms in the mood-metabolic disorders comorbidity.

2. Preliminary Data

Using the "Gene Expression in Postmortem DLPFC and Hippocampus from Schizophrenia and Mood Disorders" (dbGaP accession number phs000979.v1.p1) database, which contains microarray data from the post-mortem dlPFC (healthy controls [HC]: n = 209; patients: n = 321) and hippocampus (HC: n = 180; patients: n = 196), we conducted a hypothesis-driven analysis through the a priori selection of 12 dopamine- and 3 insulin-related genes (manuscript under review). Results showed that, in the dlPFC, after adjustment for relevant covariates, expressions of insulin receptors- (i.e. INSR, IRS1/2) and dopamine regulation-related genes (e.g. TH, DRD1-5, DAT) were influenced by body mass index (BMI), with significantly lower expression in high BMI patients with mood or psychotic disorders (Figure 1). In the hippocampus, we observed significantly lower expressions of these genes, which were not affected by BMI.

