Genes that were differentially expressed between groups were selected for mediation analyses. Diagnosis by BMI effects on expression of dopamine genes were fully mediated by expression of INSR. Analysis of conditional indirect effects showed interactions between INSR and BMI, indicating significantly stronger indirect effects at higher BMI values. In the hippocampus, we observed that expression of insulin receptor substrate 1 and 2 fully mediated the effects of diagnosis on expression of dopamine genes (Figure 2). All models were significant (e.g. DRD1: $R^2 = 0.31$, $F_{6,385} = 29.519$, p < 0.001). These results suggest that the differential expression of dopamine-related molecules in the postmortem brain of individuals with mental disorders is related to altered expression of insulin signaling genes. We also observed that obesity has region-specific moderating effects on gene expression and co-expression, supporting the hypothesis that metabolic systems are critical mediators of dopaminergic function and providing the rationale for further investigation.

Figure 1 – Mean standardized expression values of insulin and dopamine signaling genes in the dorsolateral prefrontal cortex, according to group (HC vs. MI) and obesity (BMI \geq 30 kg/m²). HC: healthy controls; MI: mental illness; BMI: body mass index.

[figure not shown]
[figure not shown]

Figure 2 – Unstandardized path coefficients for a mediation model in the hippocampus, adjusted for age, gender, race, ethanol and nicotine/cotinine. * p < 0.05; ** p < 0.001.

[name] Research Proposal Project Title: Anhedonia and the insulin pathway: a mechanistic nexus for the mood and metabolic disorders comorbidity

3. Design and Methodology

Study population: We propose to recruit 50 adults between the ages of 18 to 50 years: 25 patients with DSM-5 defined MDD or BDI/II, in a depressive episode, recruited from the Mood Disorder Psychopharmacology Unit, University Health Network, and 25 age- and sex-matched healthy controls recruited through local advertisements in the community.

Inclusion criteria (patients):

- 1. Age 18-50
- 2. DSM-5 defined MDD/BD and a total score ≥20 on the Montgomery-Åsberg Depression Rating Scale (MADRS) and no history of dementia or intellectual disability
- 3. A written, voluntary informed consent prior to study enrollment

Exclusion criteria (patients):

- 1. Use of insulin and/or oral hypoglycemiants, due to its confounding effects

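### Does the open covariate set in the group and mediation models, with its correlation screen, call for a change to the plan?

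*Combined protocol and SAP*

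**What the plan says.** All of this is in section 6 of the combined protocol and SAP unless stated otherwise.

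- **Screen.** "Clinical or demographic variables demonstrating a correlation with both biological and behavioral measures, will be assessed as potential confounders". No threshold, candidate list or entry rule is given.
- **Group models.** Mood disorder versus control effects are fitted "with age, gender, and other relevant covariates included in the models".
- **Medication and smoking.** Both are singled out for special attention, "given its potential effects of both reward processes and insulin signaling". Medication and obesity are also offered as examples of a moderator W, to be examined if appropriate. Under Potential Challenges, medication, smoking, socio-demographic, dietary and lifestyle factors are listed as confounders, to be measured systematically and then used for control, for sub-stratification or both, as suits. The same paragraph says patients' drugs will not be withdrawn.
- **Controls.** Section 3 excludes anyone with a current or lifetime psychiatric condition.
- **BMI and lipids.** Section 1 makes them part of the hypothesised abnormality: reduced insulin sensitivity and "corresponding metabolic correlates, including increased body mass index and dyslipidemia". Section 2 says "mood and metabolic disorders have a bidirectional association". The preliminary data report that gene expression values "were influenced by body mass index (BMI), with significantly lower expression in high BMI patients". Section 3 (Neural Circuits Assessment) calls for equal representation of normal-weight and obese participants, and Potential Challenges proposes stratifying on overweight or obesity.
- **Precedent.** The team's own preliminary mediation model used a short named list; the Figure 2 caption says it was "adjusted for age, gender, race, ethanol and nicotine/cotinine".

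**The concern.** Choosing covariates by their correlation with biology and behaviour is a reasonable start when the question is how biology relates to behaviour. It is less suitable for the effect of diagnosis itself. A variable can correlate with both measures simply because it stands in for diagnosis, or because it lies on the path from diagnosis to insulin signalling.

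Medication may do the first: patients stay on treatment and controls have no psychiatric history. Adjusting for it takes much of the information about diagnosis with it. BMI and lipids may do the second; if they differ between groups and drive insulin measures, adjusting for them removes part of the very path under test. Two analysts could then follow section 6 and report different group effects and different first legs of the mediation model, which the Power Analysis treats as primary.

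**Working it through.** **1. The plan's own figure.** The Power Analysis gives 116 subjects for 80% power with path coefficients of about 0.25 to 0.35. A simulation of the bias-corrected bootstrap test without covariates (1,500 trials, 1,000 resamples, two-sided 5%) gives 81–83% at 116 with paths 0.25 then 0.35, and 78% with the order reversed. The figure reproduces. With both paths at 0.30, power is 41% at 50 subjects and 95% at 150. Section 3 states 50 and section 6 states 150; that conflict is a separate matter, so both sizes are carried below.

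**2. Price of adjusting for medication.** Let p be the share of patients medicated, with no controls medicated and equal groups. Then φ² = p/(2 − p) and VIF = 1/(1 − φ²). For p = 0.8, φ² = 0.8/1.2 = 0.667 and VIF = 3.0. Power for a diagnosis-to-insulin path a = 0.30 uses a noncentral t with noncentrality a/√(1 − a²) × √(N/VIF), adjusting for age and gender. The share p is an assumption.

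| Model | VIF | SE factor | Power at N = 50 / 116 / 150 |
|---|---|---|---|
| Medication omitted | 1 | 1 | 59% / 92% / 97% |
| Adjusted, p = 0.5 | 1.5 | 1.22 | 43% / 78% / 88% |
| Adjusted, p = 0.8 | 3.0 | 1.73 | 24% / 49% / 60% |
| Adjusted, p = 0.9 | 5.5 | 2.35 | 15% / 30% / 37% |

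**3. Price of omitting it.** Suppose diagnosis has no effect and medication shifts behaviour by 0.8 SD, with 20 of 25 patients medicated. The unadjusted group difference is 0.8 × 0.8 = 0.64 SD, significant in 58% of trials. The adjusted estimate is 0.00, significant in 5%. The 95% interval half-width is 0.57 SD unadjusted and 0.98 SD adjusted.

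**4. The screen, if it were automatic.** Assume entry whenever p < 0.05 for both correlations, a biology-behaviour correlation of 0.3 given group, and medication with no effect of its own. For a 0.8 SD behavioural effect at 25 v 25, unadjusted power is 79–80%. Screened power is:

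| Medicated patients v controls | Biology effect 0.8 SD | 0.5 SD | 0.3 SD |
|---|---|---|---|
| 13/25 v 0 | 73% | 75% | 78% |
| 20/25 v 3/25 | 68% | 73% | 76% |
| 20/25 v 0 | 54% | 67% | 73% |
| 23/25 v 0 | 36% | 57% | 69% |

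The plan's path range converts to 2r/√(1 − r²): 0.52 SD for r = 0.25 and 0.75 SD for r = 0.35. The 0.8 SD column therefore lies above it. More recruits would not remove the loss within this trial's range. With 0.5 SD on both measures and 80% v 0% medicated, screened against unadjusted power is 32% v 41% at 50 subjects (9 points) and 57% v 86% at 150 (29 points).

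**5. A fixed list instead.** Five covariates that explain nothing (smoking 10 v 4, plus four neutral) take 80% to 72% at 25 v 25. Six of the twelve cells above are already at 73% or more.

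**6. BMI.** Take a true diagnosis-to-insulin effect of 0.50 SD and BMI 0.5 SD higher in patients (assumed). Entering BMI leaves 0.50 − 0.5 × 0.3 = 0.35 or 0.50 − 0.5 × 0.5 = 0.25, for BMI-to-biology slopes of 0.3 or 0.5. If BMI is equal in the two groups nothing is removed; the simulated mean under the screen is then 0.48–0.49.

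**7. Back to the text.** The screen covers clinical or demographic variables and sets them against biological ones. Section 3 files BMI and lipids under Physiological Assessment, and the confounder list in Potential Challenges omits them. Medication reaches the models through that list and the special-attention sentence, with or without the screen. Step 4 therefore describes a rule that the plan does not contain.

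**The case for a change.** The strongest reply is that the gap is real and cheap to close. No main covariate set is named for the model that the Power Analysis calls primary. Medication appears as a special consideration, a moderator and a control or stratifying variable, and these roles are not reconciled. The team has already shown that it can name a list. The screen would also be a poor safeguard on its own: if medication affects behaviour only, it would admit medication in about 5% of trials and leave the false group effect significant in 56%.

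The first part stands: the main set is not named. It also stands that, with no medicated controls, a diagnosis-by-medication term cannot be estimated. Any analyst who tries to fit it will see that, and the plan makes moderation conditional on being appropriate.

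The rest does not carry. The weak safeguard matters only if the screen is the sole route for medication, and it is not. The BMI loss needs a group difference that the obesity balancing may remove (the plan does not say whether balance holds within each group), and an entry decision that runs against the plan's own grouping of variables. Severity scales are named nowhere as covariates. Nor does a list chosen by causal role settle the matter. Diet and activity are recorded in patients who are already ill, so whether they preceded illness stays a judgement. Naming one main medication model means choosing between the losses in steps 2 and 3. The documents already allow estimates with and without medication.

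**Conclusion.** No change follows. What remains is a minor gap in pre-specification: apart from age and gender the covariates are not listed, and the choice is left to judgement that the text explicitly allows. The large power losses (for example 79–80% to 54% at 25 v 25) depend on an automatic p < 0.05 entry rule that is not in the plan, on an assumed 80% of patients and no controls medicated, and on effects above the plan's own range. They were computed with single-outcome least squares, not with the planned GEE or bootstrap mediation test.

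The underlying difficulty is the design: diagnosis and medication are only weakly separable here. Adjusting roughly multiplies the standard error by 1.73 at the assumed share; not adjusting risks a false 0.64 SD effect. Covariate wording moves the cost from one side to the other without removing it, and section 6 already states medication confounding as a key challenge for interpretation. The loss from entering BMI, 0.15 to 0.25 SD out of 0.50, arises only if BMI differs by group and is entered. The insulin-placebo contrast is within person, so none of this touches it.

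### At 116 to 150 participants, the bias-corrected bootstrap test of mediation rejects in about 6.5–8.5% of trials, not 5%, when exactly one path is zero and the other is 0.25–0.35

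*Combined protocol and SAP*

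**What the plan says.** Section 6 (Analytic Plan, Power Analysis and Approach to Potential Challenges) states: "Mediation and moderation models will be assessed using regression-based, bias-corrected bootstrap tests". For the moderated-mediation extension it repeats the method, namely "bootstrapping to determine bias-corrected (asymmetric) 95% confidence intervals for the indirect effects". It supports bootstrapping by saying that "they are also more powerful and allow for the construction of more accurate confidence intervals", and the sentence goes on to name normal-theory methods as the comparison.

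The Power Analysis paragraph of Section 6 takes mediation of anhedonic symptoms by insulin signaling as the primary hypothesis and adds: "therefore, the power analysis is based on a bias-corrected bootstrap test of mediation". It reports that "the path coefficients were mostly of medium effect sizes", at about 0.25–0.35, and that "a sample sizes of 116 is necessary to achieve 80% power". The enrolment goal there is 150. Section 3 (Design and Methodology) plans 50 participants, 25 per group.

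The plan gives no type I error or coverage figure for the bias-corrected interval, no number of resamples and no separate significance level for the mediation test. The 5% level is implied by the 95% interval. No percentile or joint-significance check is planned.

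**The concern.** An indirect effect is the product of two paths: group to mediator (a) and mediator to outcome (b). It is zero if either path is zero. A null of practical interest here has one path real and the other absent: patients differ from controls in insulin signaling, but insulin signaling does not influence anhedonia. In that situation the bias-corrected interval can exclude zero more often than its nominal level implies.

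A declared mediated effect would be the main conclusion of the study, so its error rate should be the stated one. The stated power also belongs to this particular test and would not carry over unchanged to a better calibrated one. The problem lies within a single test. The false discovery rate adjustment in Section 6 is described with the imaging analysis, and adjusting across tests would not repair one miscalibrated test.

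**Working it through.** **Inputs.** From Section 6: bias-corrected bootstrap, 95% interval, paths 0.25–0.35, 116 for 80% power, goal 150, X a two-group variable. From Section 3: 50 participants in two equal groups. Assumed, because the plan does not say: one mediator, normal errors, no covariates, X on a unit-SD scale, 1,000 resamples.

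**Model.** M = aX + e1 and Y = bM + c′X + e2. The estimate is the product of the least-squares a and b.
- Percentile limits: the 2.5 and 97.5 centiles of the bootstrap products.
- Bias-corrected limits: z0 = Φ⁻¹(share of bootstrap products below the estimate), then the centiles Φ(2z0 − 1.96) and Φ(2z0 + 1.96).

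**Step 1: the plan's own figure.** Bias-corrected power at 116, with unit residual variances unless stated:
- 0.25/0.25: 66%
- 0.29/0.29: 80.6%
- 0.30/0.30: 83.7%
- 0.35/0.35: 94.5%
- 0.25/0.35: about 77%, or 81.5% with fully standardised variables

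So 116 for 80% is reproduced at path pairs inside the stated range.

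**Step 2: rejection with exactly one path zero.** There were 10,000 trials per cell, with c′ = 0 and Monte Carlo error of about 0.3 points. Entries are bias-corrected / percentile, in %.

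| a, b | n=50 | n=116 | n=150 |
|---|---|---|---|
| 0, 0.25 | 3.5 / 1.4 | 6.5 / 3.4 | 6.7 / 3.7 |
| 0, 0.30 | 4.8 / 2.2 | 7.4 / 4.4 | 7.7 / 4.6 |
| 0, 0.35 | 6.2 / 3.1 | 7.6 / 4.6 | 7.9 / 5.3 |
| 0.25, 0 | 5.1 / 2.3 | 7.0 / 3.8 | 7.6 / 4.4 |
| 0.30, 0 | 6.2 / 3.2 | 8.2 / 4.7 | 7.9 / 5.1 |
| 0.35, 0 | 7.9 / 4.2 | 8.5 / 5.7 | 8.1 / 5.6 |

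At 116 the bias-corrected rate is 6.5/5 = 1.3 to 8.5/5 = 1.7 times nominal. It stays at 7.2–7.8% with c′ = 0.3, and one cell rerun with 5,000 resamples gave 8.4%, so more resampling does not cure it. Smaller runs at 116 gave 6.9–8.6%, 6.5–8.2% and, with the non-zero path at 0.35, 8.2–9.0%.

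**Step 3: cross-check by hand.** The joint-significance test requires both paths to be significant. With one path zero it therefore rejects with probability of about 0.05 × power of the other path, where that power is about Φ(β√n − 1.96).
- n=116, β=0.25: 0.05 × Φ(2.69 − 1.96) = 0.05 × 0.77 = 3.8%
- n=116, β=0.35: 0.05 × Φ(3.77 − 1.96) = 0.05 × 0.96 = 4.8%
- n=50, β=0.25: 0.05 × Φ(1.77 − 1.96) = 0.05 × 0.42 = 2.1%

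The simulated joint test gave 3.7–5.1% at 116. The calculation also shows why rates fall at 50: the non-zero path is itself often missed.

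**Step 4: both paths zero.** The bias-corrected interval excludes zero in 0.5–0.8% of trials.

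**Step 5: width and coverage.** Bias-corrected intervals average 1–4% wider than percentile intervals. With both paths at 0.25–0.35 and n=116–150, they miss the true value in about 4.0–5.6% of trials. The bootstrap products are skewed in the direction of the estimate, so z0 takes the sign of the estimate and both limits move away from zero. The fault is therefore one of location.

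**Step 6: power, bias-corrected against percentile.**
- n=116, standardised 0.25/0.35: 81.5% v 75.5%; other runs gave 81% v 75% and 83% v 78%
- n=116, standardised 0.30/0.30: 87% v 81%
- n=116, 0.29/0.29: 80.6% v 72.7%
- n=128, 0.29/0.29: 85.9% v 79.8%
- n=150, 0.29/0.29: 91.5% v 87.4%
- n=50, standardised 0.25/0.35 and 0.30/0.30: 40% v 29% and 41% v 29%

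**The case against.** Several points on the other side stand.

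- **The accuracy sentence in Section 6 is not shown to be wrong.** It concerns bootstrap methods in general, compared with normal-theory methods. The percentile bootstrap belongs to that class, and no normal-theory comparator was simulated. A reader might infer that the plan makes a false claim; its text does not support that.
- **The one-path null is a judgement.** The Background section, with about a two-fold diabetes risk and about 30% metabolic syndrome in mood disorders, makes a non-zero group-to-mediator path plausible. It does not establish one in this sample, which excludes users of insulin and oral hypoglycemic drugs.
- **The percentile interval is not exact.** At 116 it rejects in 3.4–5.7% of trials, some cells in other runs reach 6.0%, and at 50 it is conservative (1.4–4.2%). Part of the power gap is therefore percentile conservatism and not only bias-corrected over-rejection.
- **The simulated model is simpler than the plan's.** Section 6 adds covariates and several mediator constructs, and uses GEE for the effort task. The size of the inflation there is untested.
- **Mediation is not unambiguously primary.** Section 1 states a group difference in willingness to make effort as what is primarily hypothesized. Mediation is nevertheless what Section 6 powers and calls its main objective.

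These points limit the size and scope of the finding. They do not remove the over-rejection at the powered sample sizes.

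**Conclusion.** The point holds in a limited form. At 116–150 analysable participants, with exactly one path zero and the other at 0.25–0.35, the specified test has a false-positive rate of about 6.5–8.5% against a nominal 5%. This rests on one mediator, normal errors, balanced groups and no covariates.

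Three stronger readings should be resisted:
- **That the 95% intervals are too narrow.** They are slightly wider than percentile intervals and cover at about the nominal rate when both paths are at planned sizes.
- **That every true-null trial is affected.** With both paths zero the test is very conservative.
- **That the same inflation applies to the 50 participants of Section 3.** There the rate is about 3.5–7.9%, so inflation is modest or absent. Clearer inflation at that size appeared only with a path of 0.5 (7.8–9.4%), which is outside the planned range.

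Nor is the figure of 116 an arithmetical error. It is reproducible for the test named, but it does not give 80% under a percentile rule at the path pairs that reproduce it.

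**What to change.** In the mediation paragraph of Section 6, make the percentile bootstrap 95% interval, with a stated number of resamples (for example 5,000), or the joint-significance test the decision rule for the primary indirect effect. Keep the bias-corrected interval as supplementary.

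In the Power Analysis paragraph, name one pair of path values and their scale, and restate power for the chosen test. For the percentile interval with standardised paths at 116, power is about 75–77% for 0.25/0.35 and about 81% for 0.30/0.30. At 0.29/0.29 (unit residual variances), about 128–130 analysable participants give 80%, and 150 give about 87–88%.

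The goal of 150 need not change, provided that losses stay within 150 − 130 = 20 to 150 − 128 = 22 participants (13–15%). The plan states no dropout rate. Its present margin is 150 − 116 = 34 (23%), so the smaller margin should be acknowledged.

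The cost is a change of wording and a restated power figure: about 6 points lower at 116 for the standardised pairs (about 8 at 0.29/0.29), and about 11–12 points lower if only 50 are analysed. No new data are required.
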